Clinical Study Protocol

Drug Substance	Dapagliflozin
Study Code	D169CC00001
Version	4.0
Date	12 th November 2020

An International, Double-blind, Randomised, Placebo-Controlled Phase III Study to Evaluate the Effect of Dapagliflozin on Reducing CV Death or Worsening Heart Failure in Patients with Heart Failure with Preserved Ejection Fraction (HFpEF)

DELIVER - Dapagliflozin Evaluation to Improve the LIVEs of Patients with PReserved Ejection Fraction Heart Failure

Sponsor: AstraZeneca AB, [name]

Regulatory Agency Identifying Number(s):

Eudra CT number: 2018-000802-46

VERSION HISTORY

Version 1.0, 24th April 2018				
Initial creation				
Version 2.0, 09th May 2018				
	Section changed	Previous Version	Current Version	Reason for change
1.	Title page	Regulatory Agency Identifying Number(s):	Regulatory Agency Identifying Number(s): Eudra CT number: 2018-000802-46	Missing information added
2.	Appendix A – Section A3	A subject who is rescreened is not required to sign another ICF.	A subject who is rescreened is required to sign another ICF.	Correction of typo error
3.	Appendix D – Section D2 Correction of cross referencing error	Withdrawal of consent for genetic research: Subjects may withdraw from this genetic research at any time, independent of any decision concerning participation in other aspects of the main study. Voluntary withdrawal will not prejudice further treatment. Procedures for withdrawal are outlined in Section 7 of the main Clinical Study Protocol.	Withdrawal of consent for genetic research: Subjects may withdraw from this genetic research at any time, independent of any decision concerning participation in other aspects of the main study. Voluntary withdrawal will not prejudice further treatment. Procedures for withdrawal are outlined in Section 7 of the main Clinical Study Protocol.	Cross-reference link was updated
4.	Mislabelling of Appendices	Mislabelling of Appendices A, B, C, D, E, G, H, I, J, K, L, M	Correction of mislabelling of Appendices A, B, C, D, E, F, G, H, I, J, K, L	Typo error

Version 3.0, 16th December 2019		
	Section changed	Summary of change
1.	1.2 Synopsis	CSP synopsis was modified to adjust the study sample size from original 4700 to approximately 6100, based on ongoing blinded monitoring of events accrual. Accordingly, the anticipated recruitment period was increased from 18 months to 22 months.
2.	4.1 Overall design	Overall design was modified to adjust the sample size increase as below: “It is estimated that approximately 11000 patients at approximately 400-500 sites in 20-25 countries will be enrolled to reach approximately 6100 randomised patients.”
3	4.2 Scientific rationale for study design	The subacute subgroup definition was modified, such that the recent discharge date from hospitalisation for heart failure was extended from 21 days to 30 days, to be more aligned with clinical practice, i.e.: “...to address a specific need in a period with high risk for events, a proportion of patients will be enrolled and randomised during hospitalisation for heart failure or within 30 days of discharge from hospitalisation for heart failure (subacute subgroup).”
4.	6.3.1.2 Capping	The definition of subacute subgroup (one of the potential capping factors) was modified the same as above.
5.	9.2 Sample size determination	Statistical section 9.2 was updated to reflect the sample size increase in detail. Specifically: “Based on the ongoing blinded monitoring of event accrual (including the percentage of patients from the sub-acute category), the sample size is increased from original 4700 to approximately 6100 randomised patients to provide the required number of 844 patients with a primary event. Accordingly, the recruitment period is anticipated to increase from the original 18 months to 22 months. The study is event driven and the number of patients or duration may further change.”

Version 4.0, 12 th November 2020		
	Section changed	Summary of change
1.	1.1: Schedule of Activities (SoA)	
Concomitant Medication check was added to Visit 1 (Enrolment) to clarify screening eligibility checks.
 
Clarification to BP, pulse, weight and creatinine assessments at Visit 6 and 7 - onwards added: “Assessments to be repeated every 12 months (Visit 6, Visit 9, Visit 12)”.
 
Recording of COVID-19 testing results from Visit 2 onwards added to Safety Events.

2.	1.2 Synopsis	
Primary objective and first secondary objective were updated to include analysis of both the full study population and the subpopulation with LVEF <60%.
 
Urgent HF visits were added in addition to hospitalizations for HF as recurrent HF events to be evaluated for the first secondary objective.
 
“To determine whether dapagliflozin is superior to placebo in reducing CV death” added to secondary objectives.
 
“To determine whether dapagliflozin is superior to placebo in reducing the proportion of patients with worsened NYHA class” moved from secondary to exploratory objectives.
 
“To compare the effect of dapagliflozin versus placebo on health status assessed by Patient global impression of severity (PGIS) questionnaires” removed. Table 2 corrected accordingly.
 
Exploratory objective “To compare the effect of dapagliflozin versus placebo on EuroQol five-dimensional five-level questionnaire (EQ- 5D-5L)” was updated to:
 
“To describe health status assessed by EuroQol five-dimensional five-level questionnaire (EQ- 5D-5L)”.
 
Estimated date of last patient completed changed to: Q4 2021.
 
Study duration was prolonged to 39 months.
 
Number of primary endpoint events changed from 844 to 1117.
 
Recruitment period prolonged up to 29 months.
 
Statistical methods section updated to reflect the changes to the primary objective, multiple testing procedure and the increased event target.

3.	2.1 Study Rationale	
Section updated to reflect current amendment changes about the two hypotheses, that dapagliflozin is superior to placebo in reducing the composite of CV death and HF events (hospitalisation for HF or urgent HF visit) in patients with HF and preserved systolic function (LVEF >40%), with or without T2D, in (1) the full population and in (2) an LVEF <60% subpopulation.

4.	4.1 Overall Design	
Number of primary endpoints updated to 1117.
 
Anticipated total study duration time updated to 39 months.
 
It was added that Study Closure Visit (SCV) which should be held within 6 weeks of the PACD, can be extended if decided by Global Study Team.

5.	4.2 Scientific rationale for study design	
New paragraph added to justify the added testing of the treatment effect in patients with LVEF <60.

6.	8. Study Assessments and Procedures	It was clarified that during Visit 1, the investigator assesses patient's eligibility criteria and reviews concomitant medications, and relevant medications will be recorded. COVID-19 testing was added to Safety events assessment during Visits: 3,4,5,6,7 and onwards, as well as Premature Treatment Discontinuation Visit and Study Closure Visit. It was clarified that starting from Visit 6, vital signs (BP, pulse), and weight assessment as well as blood samples collection for creatinine (for calculation of eGFR) will be repeated every 12 months - on Visit 6, Visit 9 and Visit 12.
7.	8.3 Efficacy Assessments	An alternative phone collection mode solution was implemented for the administration of electronic PROs in settings that are affected by COVID-19 pandemic.
8.	8.4 Safety Assessments	COVID-19 testing results recording was added into Other safety assessments.
9.	8.5 Collection of adverse events	The process of Adjudication of potential DKA events by an independent DKA Committee was implemented (section 8.5.1.2.2.) Requirements for capturing of Major hypoglycaemic events were added as section 8.5.1.4.
10.	9.2 Sample size determination	Section updated to reflect the dual primary hypothesis, changed multiple testing procedure and increased event target.
11.	9.3 Populations for analysis	A subset of the full analysis set consisting of patients with baseline LVEF of <60% (or LVEF <60% subpopulation) will be analysed separately as part of the confirmatory statistical testing procedure added to full analysis set.
12.	9.4 Statistical Analyses	Analysis of the primary variable updated with dual primary analysis. Analysis of the secondary variables updated with regard to analysis of recurrent HF events and CV death for the LVEF < 60 subpopulation, and addition of time to CV death as a secondary endpoint. Methods for multiplicity control updated according to the dual primary hypotheses and updated testing procedure.
13.	9.5 Interim Analyses	Clarification added that the interim analysis testing will be done in the full study population. Futility analysis was removed.

This Clinical Study Protocol has been subject to a peer review according to AstraZeneca Standard procedures. The Clinical Study Protocol is publicly registered and the results are disclosed and/or published according to the AstraZeneca Global Policy on Bioethics and in compliance with prevailing laws and regulations.

TABLE OF CONTENTS

TITLE PAGE.....	1

1. PROTOCOL SUMMARY

1.1 Schedule of Activities (SoA)

Table 1 Study of Assessments

Visit	1 Enrolment	2 Randomisation	3	4	5	6	7 – onwards	Premature Treatment Discontinuation Visit	Study Closure Visit	For details see Section:	
Day/Month	Day -21 to Day -1	Day 1	Day 30 (±7)	Day 120 (±7)	Day 240 (±7)	Day 360 (±7)	Day 480 - onwards (every 120 days ±14 days)		≤ 6 weeks after PACD		
Informed consent	X ⁶									5.1, A 3	
Inclusion/exclusion criteria	X	X								5.1, 5.2	
Demographics	X									5.1	
Medical history	X	X								5.1	
Concomitant medication	X	X	X	X	X	X	X	X	X	6.5	
Cardiac and HF related procedures			X	X	X	X	X	X	X	8.5.1.3	
Physical exam	X	X							X	8.4.1	
Systolic and diastolic BP	X	X	X				X ³	X ³	X	X	5.2, 8.4.2
Pulse	X	X	X				X ³	X ³	X	X	5.2, 8.4.2
Weight	X						X ³	X ³	X	X	8.4.6.1
Height	X										8.4.6.1
NYHA classification	X	X	X	X	X				X	X	5.1, Appendix I
12-lead ECG	X										8.4.3

Visit	1 Enrolment	2 Randomisation	3	4	5	6	7 – onwards	Premature Treatment Discontinuation Visit	Study Closure Visit	For details see Section:
Day/Month	Day -21 to Day -1	Day 1	Day 30 (±7)	Day 120 (±7)	Day 240 (±7)	Day 360 (±7)	Day 480 - onwards (every 120 days ±14 days)		≤ 6 weeks after PACD	
C-lab NT-proBNP	X									5.1
C-lab eGFR (creatinine)	X		X	X		X ³	X ³			5.2, 8.4.4
C-lab HbA1c	X									6.3.1.1
Sample for genetic research, if applicable ⁵		X								Appendix D
KCCQ		X ⁴	X ⁴	X ⁴	X ⁴			X ⁴	X ⁴	8.3.3.1
PGIS		X ⁴	X ⁴	X ⁴	X ⁴			X ⁴	X ⁴	8.3.3.2
EQ-5D-5L		X ⁴			X ⁴			X ⁴	X ⁴	8.3.3.3
Local pregnancy test (female patients with childbearing potential only)		X								5.1
Randomisation		X								8.2.1
Dispense investigational product (IP)		X		X	X	X	X			6
Collect unused IP; check IP compliance				X	X	X	X	X	X	6

Visit	1 Enrolment	2 Randomisation	3	4	5	6	7 – onwards	Premature Treatment Discontinuation Visit	Study Closure Visit	For details see Section:
Day/Month	Day -21 to Day -1	Day 1	Day 30 (±7)	Day 120 (±7)	Day 240 (±7)	Day 360 (±7)	Day 480 - onwards (every 120 days ±14 days)		≤ 6 weeks after PACD	
Efficacy events (death and worsening heart failure) ¹		X ¹	X	X	X	X	X	X	X	8.3
Safety events ^{2,7}	X	X	X	X	X	X	X	X	X	8.4

AEs Adverse events; DAEs Adverse events leading to discontinuation of investigational product; PACD Primary Analysis Censoring Date; SAEs Serious adverse events; C-lab Central laboratory

¹ Efficacy events are considered as endpoints from time of randomisation and throughout the study. Prior to randomisation, these events are considered as SAEs.

² SAEs will be recorded from the time of informed consent. DAEs and Amputations, adverse events (AEs) leading to amputation and potential risk factor AEs for amputations affecting lower limbs will be recorded from Visit 2 onwards.

³ Assessments to be repeated every 12 months (Visit 6, Visit 9, Visit 12).

⁴ Will be administered using a site-based electronic device. It is preferred that PRO questionnaires are completed prior to any other study procedures and before discussion of disease progression to avoid biasing the patient’s responses to the questions

⁵ Blood sample for future genetic research is optional. The genetic sampling is subject to separate consent by the patient.

⁶ The Patient signs the ICF. Patients who agree to the optional sampling of blood for genetic research will provide their consent.

⁷ Including recording of COVID-19 testing results from Visit 2 onwards.

1.2 Synopsis

International coordinating Investigator

PPD

PPD

PPD

PPD

PPD

PPD

[name]

US

Protocol Title:

An International, Double-blind, Randomised Placebo-Controlled Phase III Study to Evaluate the Effect of Dapagliflozin on Reducing CV Death or Worsening Heart Failure in Patients with Heart Failure with Preserved Ejection Fraction (HFpEF).

Rationale:

The prevalence of chronic heart failure (HF) continues to increase globally, and the annual global economic burden (several hundred billion dollars in 2012) will increase as the population ages. Approximately half of all heart failure patients have heart failure with preserved ejection fraction (HFpEF) representing a particularly significant unmet need given that no approved pharmacotherapy exists specifically for this condition. Patients with HFpEF generally receive diuretic treatment for symptom relief, and should receive guideline recommended therapies for concomitant diseases such as hypertension. Recent data from cardiovascular (CV) outcome trials of SGLT2 inhibitors (empagliflozin and canagliflozin) and real world studies (including patients treated with dapagliflozin) indicate that treatment with SGLT2 inhibitors can reduce the risk of CV death and hospitalisation due to HF in patients with Type 2 Diabetes (T2D) overall and in patients with T2D and concomitant HF. Limitations associated with the randomised clinical trials as well as the observational studies are that only patients with T2D were studied, and that the proportion of patients with HFrEF and HFpEF, respectively, is unknown. This study will test the hypothesis that dapagliflozin will reduce the composite of CV death and HF events (hospitalisation for HF or urgent HF visit) in patients with HF and preserved systolic function (LVEF >40%), with or without T2D.

Table 2 Objectives and Endpoints

Primary objective:
 
To determine whether dapagliflozin is superior to placebo, when added to standard of care, in reducing the composite of CV death and HF events (hospitalisation for HF or urgent HF visit) in patients with HF and preserved systolic function in
 
 • full study population • subpopulation with LVEF <60% 	
Endpoint/variable:
 
Time to the first occurrence of any of the components of this composite:
 
 1. CV death 2. Hospitalisation for HF 3. Urgent HF visit (e.g., emergency department or outpatients visit)

Secondary objective:
 
To determine whether dapagliflozin is superior to placebo in reducing the total number of HF events (hospitalisation for HF or urgent HF visit) and CV death in
 
 • full study population • subpopulation with LVEF <60% 	
Endpoint/variable:
 
Total number of HF events (first and recurrent) and CV death

To determine whether dapagliflozin is superior to placebo in improving Patient Reported Outcomes measured by KCCQ
	
Change from baseline in the total symptom score (TSS) of the KCCQ at 8 months

To determine whether dapagliflozin is superior to placebo in reducing CV death
	
Time to the occurrence of CV death

To determine whether dapagliflozin is superior to placebo in reducing all-cause mortality
	
Time to the occurrence of death from any cause

Safety objective:
 
To evaluate the safety and tolerability of dapagliflozin compared to placebo in patients with HFpEF
	
Serious adverse events (SAEs), adverse events leading to treatment discontinuation (DAEs), amputations, adverse events (AEs) leading to amputation and potential risk factor AEs for amputations affecting lower limbs

Exploratory Objective:
 
To determine whether dapagliflozin is superior to placebo in reducing all-cause hospitalisation
	
Time to the first occurrence of hospitalisation from any cause

To determine whether dapagliflozin is superior to placebo in reducing the proportion of patients with worsened NYHA class	Proportion of patients with worsened NYHA class from baseline to 8 months
To describe health status assessed by EuroQol five-dimensional five-level questionnaire (EQ-5D-5L) to support health economic analysis and health technology assessment	Results will be reported separately in a health economic report
To determine whether dapagliflozin compared with placebo will have an effect on systolic BP	Change in systolic BP from baseline
To determine whether dapagliflozin compared with placebo will have an effect on body weight	Change in body weight from baseline
To determine whether dapagliflozin compared with placebo will have an effect on eGFR.	Change in eGFR from baseline
To explore whether dapagliflozin compared to placebo improves KCCQ summary scores, subscores of TSS (Symptom frequency and symptom burden) and domains	Change in Clinical summary score, TSS subscores, Overall summary score, QoL score
To collect and store blood samples for future exploratory genetic research	Not applicable. Results will be reported separately

BP Blood pressure; CV Cardiovascular; EQ-5D-5L EuroQol five-dimensional five-level questionnaire
HF Heart failure; HFpEF Heart failure with reduced ejection fraction; KCCQ Kansas City Cardiomyopathy
Questionnaire NYHA New York Heart Association

Overall design:

This is an international, multicentre, parallel-group, event-driven, randomised, double-blind study in patients with HFpEF, evaluating the effect of dapagliflozin 10 mg versus placebo, given once daily in addition to background regional standard of care therapy, including treatments to control co-morbidities, in reducing the composite of CV death and heart failure events (hospitalisations for HF or urgent HF visits). Adult patients aged ≥ 40 years with HFpEF (LVEF $>40\%$ and evidence of structural heart disease) and New York Heart Association (NYHA) class II-IV who are eligible according to the inclusion/exclusion criteria will be randomised in a 1:1 ratio to receive either dapagliflozin 10 mg or placebo. Both out-patients and in-patients hospitalised for heart failure and off intravenous heart failure-therapy for 24 hours can be randomised. It is estimated that approximately 11000 patients at approximately 400-500 sites in 20-25 countries will need to be enrolled to reach approximately 6100 randomised patients.

Study Period:

Estimated date of first patient enrolled: Q3 2018

Estimated date of last patient completed: Q4 2021

Number of randomised Subjects: approximately 6100 patients

Treatments and treatment duration:

Patients will be randomised in a 1:1 ratio to receive either dapagliflozin 10 mg or placebo once daily. The original anticipated average treatment duration was 24 months (range 15 to 33 months). With updated sample size and increased target number of events, the maximum treatment duration is expected to be approximately 39 months.

Data Monitoring Committee:

An independent Data Monitoring Committee (DMC) will review accumulating trial data by treatment group in order to monitor patient safety and efficacy, ensure the validity and integrity of the trial, and make benefit-risk assessment.

Statistical methods

This study is event-driven with a target of 1117 patients with a primary endpoint event. The primary objective of the study is to determine the superiority of dapagliflozin versus placebo, when added to standard of care, in reducing the composite of CV death and HF events (hospitalisation for HF or urgent HF visit). Two hypotheses will be tested simultaneously (i.e, dual primary analyses) for this primary objective: (1) in the full population and in (2) an LVEF <60% subpopulation, with alpha allocated to each test. The final alpha split will be defined in the SAP prior to the interim analysis. It is anticipated that at least 70% of the events (i.e. approximately 780 events) will be available for the LVEF <60% subpopulation. To illustrate, assuming a true hazard ratio (HR) of 0.80 between dapagliflozin and placebo, a two-sided alpha of 1.5% would yield a power of 90% for the full population and a two-sided alpha of 2.4% would yield a power of 80% for the LVEF <60% subpopulation.

Based on above assumption and ongoing blinded monitoring of events accrual, approximately 6100 patients are estimated to provide the required number of primary events in the full population during an anticipated recruitment period up to 29 months and followed until the pre-specified number of primary events has occurred. Randomisation will be stratified by presence or absence of Type 2 Diabetes (T2D).

All patients who have been randomised to study treatment will be included in the Full Analysis Set (FAS) irrespective of their protocol adherence and continued participation in the study. The primary variable is the time to first event included in the primary composite endpoint. The primary analysis will be based on the intention to treat (ITT) principle using the FAS, including events occurring on or prior to the primary analysis censoring date (PACD), confirmed by adjudication.

In the analysis of the primary composite endpoint, treatments (dapagliflozin versus placebo) will be compared using a Cox proportional hazards model with a factor for treatment group, stratified by type 2 diabetes (T2D) status at randomisation. The p-value, hazard ratio and 95% confidence interval will be reported.

[figure not shown]
Interim analysis is planned to be performed including approximately 67% of target number of adjudicated primary endpoints.

A closed testing procedure including a pre-specified hierarchical ordering of the primary and secondary endpoints will be utilized. No multiplicity control is placed on the exploratory endpoints.

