4. STUDY DESIGN

4.1 Overall design

This is an international, multicentre, parallel-group, event-driven, randomised, double-blind, placebo-controlled study in HFpEF patients, evaluating the effect of dapagliflozin 10 mg versus placebo, given once daily in addition to background regional standard of care therapy, including treatments to control co-morbidities, in reducing the composite of CV death or heart failure events.

For an overview of the study design see [Figure 1](#), [Section 1.3](#). For details on treatments given during the study, see [Section 6.1](#).

For details on what is included in the efficacy and safety endpoints, see [Section 3 Objectives and Endpoints](#).

Adult patients with HFpEF (defined for the purposes of this study as LVEF >40% and evidence of structural heart disease) aged ≥ 40 years and with NYHA class II- IV who meet the inclusion criteria, and none of the exclusion criteria, will be randomised in a 1:1 ratio to receive either dapagliflozin 10 mg or placebo. Randomised treatment should be started as soon as possible and within 24 hours after randomisation. It is estimated that approximately 11000 patients at approximately 400-500 sites in 20-25 countries will be enrolled to reach approximately 6100 randomised patients (see [Section 9.2](#)).

Study closure procedures will be initiated when the predetermined number of primary endpoints are predicted to have occurred ($n=1117$), i.e. the Primary Analysis Censoring Date (PACD). Patients should be scheduled for a Study Closure Visit (SCV) within 6 weeks of the PACD, which can be extended if decided by Global Study Team. The anticipated total study duration is approximately 39 months dependent on randomisation rate and event rate. The study duration, and the number of patients, may be changed if the randomisation rate or the event rate is different than anticipated. The study may be terminated early if a clear harmful effect of the study treatment is detected during the DMC review, or due to DMC recommendations following pre-specified interim analyses (see [Section 9.5](#)).

Data on baseline characteristics, endpoints and AEs will be collected through a validated electronic data capture (EDC) system with electronic case report forms (eCRFs).

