The event rate assumptions are based on sub analyses of the TOPCAT and I-PRESERVE studies by geographic region, NT-proBNP levels, prior hospitalisation for HF, and T2D status ([Pfeffer et al 2015](#), [Kristensen et al 2015](#), [Kristensen et al 2017](#)). The original sample size calculation (~ 4700 randomized patients) built on the assumption of an annual event rate of 9% in the placebo group for the majority of prevalent HFpEF patients, importantly all with NT -proBNP ≥ 300 pg/ml by inclusion criterion. Additionally, a subgroup of patients due to be discharged or recently discharged from a HF hospitalisation (here denoted ‘subacute’ patients) with a higher event rate is planned to be included. Assuming 20% of patients from the subacute category with an annual event rate of 24% during the first year and 9% thereafter for the remainder of the study, the original sample size of 4700 patients was estimated to provide the required number of 844 patients with a primary event during a recruitment period of 18 months and a minimum follow-up period of 15 months.

Based on the ongoing blinded monitoring of event accrual (including the percentage of patients from the subacute category), the sample size is increased from original 4700 to approximately 6100 randomised patients. Accordingly, the recruitment period is anticipated to increase from the original 18 months to 26 months. Recruitment might be marginally prolonged in a few countries to meet local targets. The study is event driven and the number of patients or duration may further change.

With the same event rate assumptions as above, assuming 11% of patients from the subacute category, approximately 6100 patients are estimated to provide the required number of 1117 patients with a primary event during an anticipated recruitment period of 26 months and a minimum follow-up period of 13.5 months (total study duration 39 months).

In addition, the expected number of patients who will be lost to follow-up is expected to be small; hence, these are not considered in the determination of the sample size.

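### Does recruitment of up to 29 months in the synopsis, against 26 months in Section 9.2, undermine the projection of 1117 events in 39 months?

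*Protocol*

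**What the plan says.** The synopsis (Section 1.2, Statistical methods) ties about 6100 patients to the required number of events "during an anticipated recruitment period up to 29 months and followed until the pre-specified number of primary events has occurred".

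Section 9.2 derives the same 1117 events from the same 6100 patients, but on a different timetable: "during an anticipated recruitment period of 26 months and a minimum follow-up period of 13.5 months (total study duration 39 months"). Its two parts add to 39.5 months, not 39. Just before this, after giving the 26-month figure, it adds: "Recruitment might be marginally prolonged in a few countries to meet local targets". It also says that the study is event driven and that patient numbers or duration may change again.

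On attrition, Section 9.2 says that "the expected number of patients who will be lost to follow-up is expected to be small; hence, these are not considered" when the trial is sized. It does not mention non-CV death.

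Section 4.1 treats the duration as provisional: "The anticipated total study duration is approximately 39 months dependent on randomisation rate and event rate". Under the same section, closure starts when 1117 primary endpoints are predicted to have occurred. Section 8.2.8 sets the primary analysis censoring date from the rate of accrued endpoints.

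**The concern.** One projection, with one sample size and one event target, carries two recruitment periods. They cannot both fit the other planning figures: 29 months of recruitment plus 13.5 months of minimum follow-up is 42.5 months, not 39. Holding the total at 39 months would cut the minimum follow-up to 10 months.

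If 29 months were the true planning figure, the expected event count at month 39 would fall below 1117. The 39-month duration and the Q4 2021 completion date would then be optimistic, and stopping on the calendar date would cost power in both primary tests. A reader might also object that non-CV death ends follow-up without a primary event and appears nowhere in the projection, which would push the error further in the same direction.

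**Working it through.** **Inputs from Section 9.2.** N = 6100, allocated 1:1 (3050 per arm). Placebo event rate 9% per year. Subacute patients are 11% of the total, with 24% in year 1 and 9% per year afterwards. HR 0.80. No loss to follow-up.

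**Assumptions not in the document.** Even accrual; the annual rates read as one-year probabilities; proportional hazards.

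**Formulas.**
- Yearly hazards on placebo: −ln(1 − 0.09) = 0.0943 and −ln(1 − 0.24) = 0.2744. On dapagliflozin each is multiplied by 0.80.
- Event probability after follow-up t: 1 − exp(−H(t)), where H is the cumulative hazard. This is averaged over entry times spread evenly on 0 to R months, with cut-off at T months.

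**Step 1: reproduce the plan's figure (R = 26, T = 39.5).**

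| Group | Patients | Mean probability | Events |
|---|---|---|---|
| Placebo, subacute | 335.5 | 0.3207 | 107.6 |
| Placebo, other | 2714.5 | 0.1866 | 506.5 |
| Dapagliflozin, subacute | 335.5 | 0.2663 | 89.3 |
| Dapagliflozin, other | 2714.5 | 0.1525 | 414.0 |

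The total is 1117.5 (before rounding of the rows) against the stated 1117. The same method gives 849 for the earlier 4700-patient plan, stated as 844. Reading the rates as hazards gives 1062 and 801, which fit neither figure, so the one-year-probability reading is the better one.

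**Step 2: change only the timetable.**

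| Recruitment | Cut-off | Events | Against 1117 |
|---|---|---|---|
| 26 months, even | 39.5 | 1117.5 | +0.5 |
| 26 months, even | 39 | 1099.9 | −17.1 |
| 29 months, even | 39.5 | 1062.4 | −54.6 |
| 29 months, even | 39 | 1044.4 | −72.6 |

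Of the 73 events missing in the last row, about 18 (1117.5 − 1099.9) come from writing 39.5 as 39. At the same cut-off, the effect of recruitment is about 55 events.

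**Step 3: read 29 months as an outer limit.** Most patients enter evenly over 26 months, and a share enters evenly in months 26 to 29. The shares are assumed, since the protocol gives none.

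| Share entering after month 26 | Events at 39.5 months | Short of 1117 | Month when 1117 is reached |
|---|---|---|---|
| 2% | 1106.8 | 10 | 39.8 |
| 5% | 1090.9 | 26 | 40.2 |
| Even over 29 months (3/29 = 10.3%) | 1062.4 | 55 | 41.0 |

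Against 39.5 months, the delays are 0.3, 0.7 and 1.5 months.

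**Step 4: power.** By Schoenfeld, power = Φ(½√d·|ln 0.80| − z), where z is the upper α/2 normal quantile.
- d = 1117, two-sided 1.5%: Φ(3.729 − 2.432) = 90.3%.
- d = 0.7 × 1117 = 782, two-sided 2.4%: Φ(3.120 − 2.257) = 80.6%.
- A stop at 1044 events would give 88.0% and 77.6%. No rule in the protocol stops the trial at 39 months whatever the count, so these two figures do not describe the planned trial.

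**The case for a change.** The strongest case for a change is that both figures stand in current text, that only one of them reproduces the target closely, and that the protocol never says 29 months is the limit of the marginal extension. Even on that generous reading a shortfall remains at the stated date: 2% or 5% late entry gives 1089 or 1073 events at 39 months. Harmonising the text would be cheap. All of this is correct. What does not follow is any consequence for the trial beyond a few weeks of calendar time, which Section 4.1 already leaves open.

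The second argument is non-CV death. At an assumed 2% to 4% per year, the plan with 26 plus 13.5 months yields 1094 to 1071 events, and 1117 arrives at about month 40.2 to 40.9; with even accrual over 29 months it arrives at 41.8 to 42.5. The protocol gives no such rate. Nor does it show whether the 9% and 24%, taken from sub-analyses of earlier trials, are observed incidences that already reflect competing deaths or are net of them. If they are observed incidences, a further deduction counts those deaths twice. The point cannot be settled from the document, and it too would affect duration only.

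The completion date does not decide the matter either. It is stated as a quarter, counted from a first enrolment that is also stated as a quarter. Q3 2018 to Q4 2021 spans anything from 36 to 42 months, so a slip of 0.3 to 0.7 months does not show that it fails.

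**Conclusion.** The mismatch is real but clerical, and no change to the plan follows. The natural reading is a main recruitment period of 26 months with a small tail ending by month 29. On that reading the projection is about 10 to 26 events short at 39.5 months, and the target is reached 0.3 to 0.7 months later. The upper bound, with all 6100 patients entering evenly over 29 months, is 55 events and 1.5 months.

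Because the trial closes on 1117 events, the shortfall becomes time and not lost information. The event target, the sample size, the alpha levels, the power of about 90% and 80%, the analysis and the conclusions all stay the same. A team running the trial will project the closing date from actual accrual and blinded event counts, as the protocol provides, and will not rely on either planning figure.

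This rests on even accrual within each period, the Section 9.2 event rates, HR 0.80 and assumed late-entry shares of 2% to 5%. It would need another look only if closure were fixed to a calendar date.
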